**Use of sublingual tacrolimus in adult blood and
marrow transplant patients: a pilot study**

NCT# NCT04041219

16-MAY-2019

Department of Pharmacy
Research Proposal

Use of sublingual tacrolimus in adult blood and marrow transplant patients: a pilot study

Principal Investigator

[name]

Co-Investigators

[name]
[name]

Protocol Version: 2.0
Protocol Version Date: 16-May-2019

Abstract

Barriers to oral (PO) tacrolimus in recipients of an allogeneic blood or marrow transplant (BMT) are not uncommon and often result in reliance on intravenous (IV) tacrolimus, a formulation which is fraught with concerns. Sublingual (SL) administration of tacrolimus is widely used as a safe and effective alternative in the solid organ transplant population. Similar benefits may be appreciated by patients undergoing BMT, including avoidance of risks and expense associated with IV tacrolimus, as well as reduced pill burden and limited trough variability relative to PO tacrolimus. This study will establish feasibility and gather preliminary data on the dose conversion ratio of PO to SL tacrolimus through comparison of trough concentrations drawn during PO and SL tacrolimus delivery during routine laboratory monitoring. Results will be used to inform future studies in larger cohorts and assist in determining an accurate conversion ratio, which is imperative to inform clinician decision-making and allow for prescription of doses which result in trough levels that ensure the safety and efficacy of tacrolimus.

Specific Aims

- 1) Demonstrate feasibility of SL administration of tacrolimus in blood and marrow transplant (BMT) patients
- 2) Gather preliminary data to determine the conversion ratio of oral (PO) to sublingual (SL) administration of tacrolimus needed to achieve equivalent whole blood concentrations in BMT patients

Background and Significance

Tacrolimus is a calcineurin inhibitor frequently used in the prevention of graft-versus-host disease (GVHD) in recipients of an allogeneic blood or marrow transplant (BMT).^(1–5) Unfortunately, barriers to oral (PO) medication administration are not uncommon in this population and include severe mucositis, dysphagia, altered mental status, intubation without oral access and high-output diarrhea. In such cases, clinicians are often forced to rely on intravenous (IV) administration of tacrolimus, a formulation which is fraught with concerns. Studies describe higher rates of nephrotoxicity and neurotoxicity with IV compared to PO tacrolimus and reports of life-threatening cardiac arrhythmias and anaphylaxis to the castor oil component exist.^(6–9) An alarmingly high rate of PO to IV dose calculation errors has been described, likely due in part to inconsistent reports of dose conversion ratios.⁽¹⁰⁾ Additionally, dilution of the concentrated IV product to the appropriate dose is challenging and administration requires extended infusion times of 12 to 24 hours to minimize fluctuations of blood levels. This can complicate administration of other medications in patients with limited IV access and also result in erroneous reporting of blood concentrations, should blood for assay be taken from the line in which tacrolimus is being infused. The IV product is also more costly than other formulations and thus increases healthcare expenses for institutions and patients alike.^(11,12) At Mayo Clinic, the institutional cost of doses <5 mg is \$330 per day, compared to \$0.98 per 1 mg oral capsule. It is for these reasons an alternative to IV tacrolimus administration is desirable.

Sublingual (SL) administration of tacrolimus is widely used as a safe and effective alternative to the IV product in the solid organ transplant (SOT) population.^(12–17) It has been adopted routinely in the heart, lung and abdominal solid organ transplant practices at Mayo Clinic in Rochester. More recently it has been used successfully in the prevention of GVHD in pediatric transplant patients.⁽¹⁸⁾ Tacrolimus can be administered sublingually by opening a capsule and placing the contents under the tongue, with patients instructed not to swallow until after dissolution occurs and avoid eating, drinking

or suctioning of secretions for the subsequent 15 to 30 minutes.(10–12,14,16,18,19) Patients were able to achieve goal trough levels using SL tacrolimus with minimal, if any, reported adverse effects. Published literature indicates the area under the blood-concentration-time curve (AUC) for SL tacrolimus is well correlated with whole blood trough levels, the current standard of care for therapeutic drug monitoring and guidance of dose adjustments to maintain concentrations within the desired therapeutic window.(11,12) In addition to serving as a safe and effective alternative to IV administration in patients who become intolerant of oral medications, the SL formulation offers advantages over PO tacrolimus as well. When administered orally, tacrolimus has poor bioavailability (approximately 25%) due to extensive first-pass metabolism and P-glycoprotein efflux.(20) These concerns are mitigated with SL administration, which allows for direct absorption into the blood. Avoidance of first-pass metabolism may also minimize the degree of interaction between tacrolimus and drugs that effect hepatic cytochrome P-450 enzymes.(18) Reduced doses with SL administration can also decrease pill burden and cost associated with tacrolimus use.(12,15,16) Studies undertaken to determine the optimal SL to PO dose conversion ratio in SOT patients report slightly variable results depending on the type of organ received,(10–12,14,16) with most centers recommending a ratio of 1:1 or 1:2.(17) Given that enteral and first-pass hepatic metabolism are bypassed with the SL route, one report suggests that a ratio of 1:1 be used when major drug interactions are present.(14)

While the volume of data surrounding SL tacrolimus is growing in SOT, published reports describing its use in BMT are extremely limited and entirely lacking in an adult BMT population. Determination of the feasibility of administration and pharmacokinetic parameters in this cohort is an essential exploratory step toward establishing SL administration as an alternative to IV tacrolimus for patients undergoing BMT who are unable to tolerate the PO formulation. The purpose of this study will be to gather preliminary data related to feasibility and dose conversion with SL administration in clinically stable adult BMT patients. Results will be used to in future studies evaluating use of SL tacrolimus in peri-transplant and hospital settings, where IV tacrolimus is used in patients intolerant of PO tacrolimus. Determining an accurate conversion ratio is imperative to inform clinician decision-making and allow for prescription of doses that result in trough levels which ensure both safety and efficacy.

Preliminary Studies

Prior studies using SL tacrolimus in the SOT population have been conducted in patients with varying degrees of illness and in numerous settings. They investigate both transient and long-term use SL tacrolimus in the inpatient and outpatient environment. These demonstrate patients are able to achieve goal trough levels using SL tacrolimus with limited adverse effects, which are confined to adverse taste. The SL formulation shows excellent bioavailability due to direct absorption into the bloodstream and an AUC that is well correlated with whole blood trough levels. To date there is a single 5-patient case series describing SL tacrolimus use to achieve safe and effective trough concentrations in pediatric BMT patients. Doses ranged from 0.025-0.078 mg/kg/day in divided doses.

Research Design and Methods

Overview

This is a prospective, single-center, crossover, pilot study of consecutive patients undergoing allogeneic blood or marrow transplantation (BMT) at Mayo Clinic in Rochester Minnesota. It will include adult (age ≥18 years) patients prescribed tacrolimus for treatment or prevention of graft-versus-host disease (GVHD) who transition between

orally administered tacrolimus and the sublingual (SL) route of administration. We will report feasibility of the SL formulation in the population and preliminary data on the SL:PO dose conversion ratio.

Setting

This study will be conducted in Rochester, Minnesota, where Mayo Clinic completes over 700 blood or marrow transplants per year, approximately 20% of which are allogeneic transplants. Around half of these will receive tacrolimus for GVHD prevention. As a referral center, patients are diverse with respect to diagnosis and demographics. Comprehensive care is provided by a multidisciplinary treatment team including physicians from a variety of medical specialties, advanced practice providers, pharmacists, nurses, dieticians, care coordinators and social workers. Integrated inpatient and outpatient care allows for close monitoring of patients throughout the care continuum, with near-daily appointments and twice weekly tacrolimus laboratory monitoring conducted locally through day +30 following transplant or longer, as dictated by a patient's medical course.

Identification of Study Subjects

Individuals will be identified from within the adult allogeneic BMT program at Mayo Clinic in Rochester, Minnesota. Participants will **include** adults prescribed tacrolimus for treatment or prevention of GVHD. Vulnerable populations, patients with contraindications to tacrolimus, inclusive of hypersensitivity, history of posterior reversible encephalopathy syndrome or calcineurin-inhibitor induced thrombotic microangiopathy, and those lacking the capacity to consent in English and declining to participate in research will be **excluded**.

Patients will be screened when scheduled for their pre-transplant pharmacist visit. Those meeting inclusion and exclusion criteria will be enrolled during a regularly scheduled pre-transplant clinic appointment. Here they will be supplied with HIPAA Authorization and consent forms. The consent form will describe the purpose of the study, the procedures to be followed, and the risks and benefits of participation. A copy will be given to each participant and this fact will be documented in the participant's record. Fifteen minutes, or additional time as necessary, will be allowed for discussion and patient questions. Patients will be informed their care will not be impacted by declining to participate in the study.

Definitions

Dose-adjusted conversion ratio of SL and PO tacrolimus (16):

- Calculated using the concentration-to-dose ratios for each route of administration
- $[(\text{Blood concentration}_{\text{SL}}/\text{daily dose}_{\text{SL}})/(\text{Blood concentration}_{\text{PO}}/\text{daily dose}_{\text{PO}})]$

Steady state trough: obtained following stable/unchanged dosing for a minimum of 4 dosing intervals (ie, prior to the 5th scheduled dose at the earliest)

Major drug interactions with tacrolimus, ie strong CYP3A4 inhibitors and inducers

- Inhibitors: azole antifungals, macrolide antibiotics, protease inhibitors (ex. ritonavir, boceprevir) and
- Inducers: antimycobacterials (ex. rifabutin, rifampin), anticonvulsants (phenytoin, carbamazepine and phenobarbital)

- Data including new start or dose changes made in the 7 days preceding a steady state trough level for either route of administration will be collected for purposes of a secondary analysis

Hepatic dysfunction: liver function tests (AST or ALT) >3x the upper limit of normal or any stage of cirrhosis documented as part of the patient's electronic health record (EHR).

Study Procedure

Enrolled patients will enter the study at their pre-transplant clinic appointment in the outpatient setting, with tacrolimus started at day -3 prior to transplant. Prescribers will issue a prescription for tacrolimus in the usual way and the recommended starting dose will be in accordance with the established protocol (0.04 mg/kg/dose of ideal body weight), initially administered sublingually. In accordance with current protocols and standards of care, additional dose adjustments may be made at the discretion of the treating provider or consulting pharmacist based on their clinical assessments. A pharmacist or member of the investigative team will provide consultation to assist with this process. At this time the patient will also be provided with a drug diary for recording the dose (in milligrams), time, and route of administration for each dose taken.

Around allogeneic transplant, as standard of care patients are maintained on tacrolimus with therapeutic drug monitoring performed through collection of whole blood trough levels a minimum of twice weekly, or at steady state after a dose change, to ensure concentrations are within the desired therapeutic window. For the purposes of this study, enrolled patients will begin administering their existing tacrolimus capsules sublingually. Patients and caregivers will be educated to open the capsules and place the entire contents under the patient's tongue. Patients will be instructed not to swallow until absorption is complete (typically within 1-2 minutes) and avoid eating and drinking 15 minutes following administration. Doses should be given at 12-hour intervals. Patients and caregivers will be instructed to record the day, time and route of each dose in a drug diary for review by providers or pharmacists at subsequent clinic visits (Appendix A).

The dose titration and monitoring process will not deviate from usual care in this setting. Determination of goal trough level and dose changes will be at the discretion of the treating provider and not influenced by this study. Trough levels will be drawn Mondays and Thursdays, or at steady state after a dose change, as a component of routine lab monitoring. This is consistent with standard of care and usual post-transplant procedure, meaning no additional blood samples will be required for completion of this research. Should a sub- or supra-therapeutic trough be discovered in advance of this and the tacrolimus dose adjusted, 4 dosing intervals will be required on the new dose before a trough concentration will be used in study analysis. The same is true if a dose is withheld or missed in accordance with provider instructions or patient report. At each patient encounter, the provider seeing the patient will inquire about potential barriers to SL administration and record patient responses on a study data collection form (Appendix B), as well as review the patient's drug diary for any missed doses. Both the data collection form and drug diary will be scanned into the patient's EHR. Should the patient not provide their drug diary at the time of the clinic visit, a detailed history will be recorded by the provider and assessed for compliance. Only trough levels drawn during periods of full compliance will be used for study purposes. Study personnel will be available via pager to assist providers with dose adjustments based on lab results as they become available and changes will be communicated to patients in the usual

manner, either by phone or through the patient online portal. Study personnel will also be available as a resource for patients or providers during appointments if needed. Patients are instructed to contact a provider via a 24-hour phone line or through the online patient portal in the event of questions or concerns.

Cross-over to orally administered tacrolimus can occur immediately after a steady-state trough has been obtained on the initial dosage form, or as dictated by the patient's clinical status and ability to tolerate the alternative route of administration. Doses may be chosen based on provider discretion in light of drug interactions, clinical status and initial trough information. A subsequent tacrolimus trough will be obtained on PO tacrolimus in the same manner in which it was measured during the 1st phase, after which point the study period will conclude.

Data Collection

Demographics including age, gender, underlying hematologic diagnosis, type of allogeneic transplant (related, unrelated, or cord blood) and source (peripheral blood or bone marrow) will be collected from the EHR. Conditioning regimen, existing drug interactions, comprehensive GVHD prophylaxis strategy, diagnosis of hepatic dysfunction, and date of transplant will be reported. The new introduction or dose change of a medication with major interaction with tacrolimus (see "Definitions" above) within the 7 days prior to study entry or during enrolled will be noted.

Daily tacrolimus dose, reasons for withholding (if applicable), and patient-reported barriers to SL administration will be recorded. Trough levels for each route of administration will be collected after at least 4 consecutive doses for determination of the SL to PO conversion ratio.

Outcomes and Analysis

The primary endpoint is documentation of feasibility of SL tacrolimus administration in BMT patients. The secondary endpoint will be to determine the conversion ratio of SL:PO administration of tacrolimus, normalized for dose. Descriptive statistics will be reported related to remaining data including existing drug interactions and comprehensive GVHD prophylaxis strategy.

Patient report of barriers to administration of SL tacrolimus will be used to investigate feasibility of the SL formulation. These could include poor tolerability of the SL route, lack of understanding related to the administration instructions, or inability to refrain from eating or drinking for the defined amount of time. As described in "Study Procedure", these will be recorded at each clinic appointment when the patient sees a provider during the study timeframe. Per-protocol analysis will be conducted to determine the conversion ratio of SL and PO administration. Median dose conversion ratios will be compared between patients with new major drug interactions or undergoing dose changes of these medications and the remainder of the cohort.

We aim to include a total of 10 patients for analysis. This represents approximately 10% of the number needed to determine in future study the true conversion ratio with a 10% margin of error (n = 97 patients), assuming an estimated conversion ratio of 0.5 (extrapolated from available literature in the SOT population). Continuous data will be described using median (IQR). The conversion ratio of SL:PO administration of

tacrolimus will be calculated as described above for each patient (note that this is adjusted for the daily dose administered). Each subject will serve as his or her own control. The median will be determined for the cohort and by subgroup, as described in the paragraph above.

Data Storage

Data will be extracted from the EHR by select study personnel and stored in a password-protected Research Electronic Data Capture (REDCap) database. This platform meets the requirements of the Health Insurance Portability and Accountability Act of 1996 (HIPAA) compliance, with password protection and the ability to assign access levels that ensure tightly regulated data sharing. All source data will be de-identified so that only a unique study number bearing no relationship to personal identifiers will be used to identify participants. Only the investigators involved in the collection and analysis of the data will have access to information with individually identifiable private information about the human subjects. Reported data will be de-identified and presented only in composite form.

Potential Risks and Benefits to Patients

Potential risks to study participants are minimal and comparable to those of PO tacrolimus. Sublingual administration specifically has been well-tolerated in numerous reports with limited to no side effects. Reports are inclusive of a wide variety of patient populations, such as adult and pediatric patients and in lung, liver, kidney and blood and marrow transplant settings. At present, no study reports a serious side effect related to SL tacrolimus use and outcomes do not suggest risks for any adverse effects are elevated when comparing SL to PO tacrolimus. Possible unique side effects include metallic or bitter taste of the medication. Serum trough levels may fluctuate within or outside of the therapeutic window when switching between SL and PO formulations, but are monitored closely. Similar fluctuations can also occur as a part of routine treatment with PO tacrolimus due to changing clinical status, interacting medications or dietary intake. Risks in the acute care setting associated with tacrolimus use via any route include peripheral edema, pruritus, constipation, diarrhea, nausea, vomiting, anemia, changes in leukocyte count, thrombocytopenia, headache, tremor, paresthesia, and increased serum creatinine. More serious yet uncommon adverse events include liver and renal toxicity, posterior reversible encephalopathy syndrome, infection, seizure, or hemolytic uremia syndrome. No additional risk for these adverse events is conferred with the use of SL tacrolimus (relative to oral) based on the available literature. Additionally, numerous data demonstrate the safe and effective use of tacrolimus in blood and marrow transplant for GVHD. It remains a cornerstone of internationally ratified guidelines as well as Mayo Clinic clinical practice. Patients will be closely monitored by a multidisciplinary medical team, who are well-educated on the risks, as part of the standard of care procedures. Other risks associated with blood and marrow transplant exist and are expected but will not be captured as a part of this research. No additional clinic visits, blood sampling, or medication will be required for completion of this study, thus no cost is associated with the transition to SL tacrolimus.

Potential benefits to study participants include reduced pill burden and decreased intra-patient variability of trough levels, due to the ability of SL administration to bypass first-pass hepatic metabolism and drug efflux from the P-glycoprotein in the intestine. Significant scientific gains may be appreciated through demonstration of feasibility for this route of medication delivery. Initial data will illuminate a PO to SL conversion ratio which can be tested in a larger cohort of outpatients and extrapolated to environments in

which IV tacrolimus is currently used, most notably the peri-transplant period and inpatient environment. Determination of this ratio will improve clinicians' ability to prescribe doses that result in trough levels that ensure safety and efficacy when transitioning patients to SL tacrolimus.

Data Safety and Monitoring

The principal investigator (PI) or designated co-investigator will ensure screening was compatible with inclusion and exclusion criteria and confirm documentation of informed consent within 24 hours of patient enrollment. The PI or designated co-investigator will be informed of concerns by providers directing patient care as they occur and review records within 24 hours of notification. The PI will be responsible for ensuring participants' safety on a daily basis. This includes assuring routine trough monitoring for safety and efficacy is performed, weekly review of new records for potential adverse events related to SL administration of tacrolimus and reporting of serious adverse events and unanticipated problems to the Institutional Review Board (IRB).

References:

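### The conversion-ratio formula yields the reciprocal of the SL:PO dose ratio that the Overview promises, and the planning value of 0.5 is not on the formula's scale

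*Combined protocol and SAP*

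**What the plan says.** The single protocol document describes the conversion ratio in several places.

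- **Definitions.** The ratio is "Calculated using the concentration-to-dose ratios for each route of administration". The printed formula is (C_SL/D_SL)/(C_PO/D_PO), where C is the blood concentration and D the daily dose. It is attributed to reference 16.
- **Overview (Research Design and Methods).** The study will report "preliminary data on the SL:PO dose conversion ratio".
- **Outcomes and Analysis.** The ratio is the secondary endpoint, described as SL:PO and normalised for dose. The section returns to the Definitions formula: the ratio for "tacrolimus will be calculated as described above for each patient (note that this is adjusted for the daily dose administered"). Cohort and subgroup medians follow.
- **Outcomes and Analysis, sample size.** The pilot's 10 patients are set against a future study "with a 10% margin of error (n = 97 patients), assuming an estimated conversion ratio of 0.5". The 0.5 is said to come from the solid organ transplant literature.
- **Background and Significance.** That literature is introduced as "Studies undertaken to determine the optimal SL to PO dose conversion ratio in SOT patients", with "most centers recommending a ratio of 1:1 or 1:2". The same paragraph adds: "Reduced doses with SL administration can also decrease pill burden and cost associated with tacrolimus use".
- **Data Collection.** Troughs are "collected after at least 4 consecutive doses for determination of the SL to PO conversion ratio".
- **Specific Aims, and Potential Risks and Benefits to Patients.** Both give the order as PO to SL.

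**The concern.** The formula compares exposure per milligram between routes, with SL in the numerator. A dose conversion ratio compares the doses needed for the same exposure. The two run in opposite directions: if SL delivers more exposure per milligram, the exposure ratio exceeds 1 and the SL:PO dose ratio falls below 1. The plan computes the first and, in the Overview, names the second. Its planning value of 0.5 also belongs to the second.

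The ratio is the named secondary endpoint. The plan says it will inform later studies and help clinicians choose doses when changing route. The risk is that a reported median is read in the wrong direction, or set beside 0.5 as if the two were on one scale.

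**Working it through.** **1. The plan's own figure.** The only computed figure that uses the 0.5 is n = 97. Inputs from Outcomes and Analysis are a ratio of 0.5 and a margin of 10%. The confidence level is not stated, so I assume two-sided 95%.

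n = z² × p(1 − p)/d² = 1.96² × 0.5 × 0.5/0.10² = 96.04, rounded up to 97.

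The figure reproduces, but only with 0.5 treated as a binomial proportion and the margin taken as absolute. A 90% level gives 68, and a relative margin (d = 0.05) gives 385. The formula does not suit a continuous ratio in either direction. At a value of 2.0, p(1 − p) = −2 and n is about −768, which is meaningless. So 97 says nothing about which direction was intended; it is a separate fault in the same sentence.

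**2. What the formula measures.** Set C_SL = C_PO = C:

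(C/D_SL)/(C/D_PO) = D_PO/D_SL.

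This is the reciprocal of D_SL/D_PO.

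**3. A worked patient (illustrative numbers).** C = 8 on both routes, D_SL = 3, D_PO = 6.

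- Definitions formula: (8/3)/(8/6) = 2.0 = D_PO/D_SL.
- SL:PO dose ratio: (8/6)/(8/3) = 0.5 = D_SL/D_PO.

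**4. The Background's literature range on each scale.** The 0.75 row is an illustrative midpoint.

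| True SL:PO dose ratio | Definitions formula | Formula value ÷ SL:PO dose ratio |
|---|---|---|
| 1.0 (1:1) | 1.0 | 1 |
| 0.75 | 1.33 | 1.78 |
| 0.5 (1:2) | 2.0 | 4 |

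The last column is the error made by someone who reads the formula's value as an SL:PO dose ratio.

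**5. Where 0.5 sits.** It is one end of the literature range as an SL:PO dose ratio (0.5 to 1.0). It lies outside the range on the formula's scale (1.0 to 2.0). As a formula value, 0.5 means D_SL/D_PO = 1/0.5 = 2.0, an SL dose twice the PO dose. That contradicts the Background's statement on reduced SL doses and the reduced pill burden listed among the potential benefits.

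**6. Direction of each statement.**

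- Agree with the formula on the dose scale: Specific Aims, and Potential Risks and Benefits (PO to SL).
- Can be read as agreeing: the endpoint wording in Outcomes and Analysis (SL over PO, normalised for dose).
- Readable either way: Data Collection, which keeps the Background's SL to PO order but omits the word dose.
- Opposite to the formula: the Overview label and the 0.5.

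**The case against.** The strongest reply is that the estimator is fully specified. Every term in the formula carries its route, and Outcomes and Analysis ties the SL:PO endpoint label to that formula. On this reading the label means SL over PO exposure per unit dose, the PO to SL wording elsewhere agrees, and the clear conflicts shrink to one word in the Overview and one planning value. In addition, 0.5 serves only to size a hypothetical later study, and the pilot result is never tested against it. The factor of 4 needs a reader who ignores the printed formula and a true ratio at one end of the range. Doses and troughs are kept for each route, so any patient's value can be inverted later.

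Much of this stands. An analyst following the formula will compute one definite number, 0.5 is not a success criterion, and the size of the error is conditional. The plan also already calculates the ratio per patient before taking medians, so that needs no change.

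The contradiction remains. Reading the endpoint as exposure per unit dose does not rescue the Overview, which says dose conversion ratio. It makes 0.5 worse, because 0.5 would then mean lower SL exposure per milligram. No single reading reconciles the formula, the Overview label and the assumed value.

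**Conclusion.** The concern holds. The formula gives the reciprocal of the SL:PO dose ratio named in the Overview, and the assumed 0.5 corresponds to 2.0 on the formula's scale. The algebra rests only on equal troughs. Placing 0.5 on the dose scale rests on the Background's 1:1 and 1:2 being SL to PO, the order in which they are introduced.

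The consequence is a possible misreading by a factor of 1 to 4 over the literature range. It depends on the true ratio and on the reader taking the value as an SL:PO dose ratio; at the plan's own expectation of 0.5 the factor is 4. Doses within the trial follow provider judgement and measured troughs, so patient management, the data collected and the target of 10 do not depend on this. It should be corrected because it concerns the definition of a named endpoint meant to guide later work, and the correction is cheap.

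**What to change.** Reconcile the sections to one labelled direction. Either option is valid, and neither implies a view on which dose ratio is clinically right.

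- **(a) Keep the formula.** In Definitions, label it as the dose-normalised exposure ratio SL/PO, equal to the PO:SL dose ratio at equal troughs. Correct the Overview label and clarify the wording in Data Collection and in the endpoint statement. Beside the 0.5, state that a literature SL:PO dose ratio of 0.5 is 2.0 on this scale. This is the lighter repair, because it leaves the cited definition and the aims intact.
- **(b) Report the SL:PO dose ratio.** Define it as (C_PO/D_PO)/(C_SL/D_SL). Align Specific Aims, Data Collection, Outcomes and Analysis, and Potential Risks and Benefits. Note that this is the inverse of the formula attributed to reference 16.

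Under either option, keep the planned order: ratio per patient, then the median. Inverting a finished median is not quite the same with an even number of patients. If the two middle values were 1.6 and 2.4 (illustrative), the median is 2.0 and its inverse 0.500, whereas the median of the inverted values is (0.625 + 0.417)/2 = 0.521, about 4% higher.

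Separately, replace the n = 97 sentence with a precision calculation for a continuous ratio. The plan gives no SD, so only a range can be shown. For a mean on the formula's scale at 95% confidence, n = (1.96 × SD/margin)². Assumed SDs of 0.25 to 1.0 give 25 to 385 patients for a margin of 0.10, and 7 to 97 for a margin of 0.20 (10% of 2.0). On the log scale, with a ±10% relative margin and an assumed CV of 30% to 60%, n = (1.96 × √ln(1 + CV²)/ln 1.1)² gives 37 to 131.

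The cost is wording in a handful of sections. No extra data, visits or patients are needed, since the dose and a trough for each route are already collected.
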